12.3. Appendix 3: Risk Assessment

Potential Risk of Clinical Significance	Summary of Data/Rationale for Risk	Mitigation Strategy

Excessive erythropoiesis leading to thrombosis and/or tissue ischemia
	
In animal studies, excessive erythropoiesis (Hgb/Hct > upper limit normal) attributed to daprodustat was associated with vascular congestion, microthrombi, and tissue ischemia in a number of organs.
 
In the phase 2 proof of concept study, a high incidence of discontinuation due to hemoglobin stopping criteria (Hgb > 13.5 g/dL or Hgb increased > 1 g/dL over any 2-week period) was observed. In non-dialysis subjects administered 10 mg, 25 mg, 50 mg or 100 mg of daprodustat daily, a total of 21 of 61 subjects (34%) met these criteria. In hemodialysis-dependent subjects administered either 10 mg or 25 mg of daprodustat daily, a total of 8 of 31 subjects (26%) met these criteria.
 
Phase 2 dose-ranging studies, and associated statistical and dose response modelling has informed Phase 3 dose rationale, starting doses, dose steps, and dose adjustment scheme to optimize Hgb management.
 
Integrated AE data [including 2 global phase 2b studies (24-week treatment duration) and 2 Japanese phase 3 studies (52-week treatment duration)]: Few subjects experienced a possible thrombosis related adverse event in the setting of excessive erythropoiesis [3/688 (0.5%) subjects on daprodustat vs. 0/404 on rhEPO].
 
Following review of clinical data received to date, this has not been identified as a safety concern for daprodustat when dose is managed appropriately according to target Hgb. However, experience with daprodustat is currently insufficient to fully characterize this risk.
	
 • Specific eligibility criteria related to requirements for entry Hgb are detailed in Section 6.2.1. • Hgb will be closely monitored throughout the dosing period as outlined in the SoA Table Section 2. • Specific guidance for discontinuation of daprodustat based on achieved Hgb is provided in Section 8.2.1.1. • Monitoring of emerging safety data by an internal GSK Safety Review Team.

Worsening hypertension
	
In a dog cardiovascular study, single oral doses of daprodustat (up to 90 mg/kg) did not produce effects on blood pressure.
 
Marketed rhEPO and its analogues have been associated with risks related to uncontrolled hypertension, including the need for initiation of or increases in antihypertensive therapy when used in patients with
	
 • Specific eligibility criteria related to blood pressure, including exclusion of subjects with uncontrolled hypertension, are detailed in Section 6.2 .

Potential Risk of Clinical Significance	Summary of Data/Rationale for Risk	Mitigation Strategy
	
anemia of CKD (i.e. 25% Epogen, 27% Mircera, and 40% Aranesp treated patients with renal anemia required initiation or increase in their anti-hypertensive medications; hypertensive encephalopathy and seizures have been reported. The contribution of rhEPO-associated hypertension to the unfavourable effects on cardiovascular outcomes remains uncertain).
 
Integrated AE data from clinical trials with daprodustat [including 2 global phase 2b studies (24-week treatment duration) and 2 Japanese phase 3 studies (52-week treatment duration)]:
 
 ○ The majority (>90%) of subjects had baseline history of hypertension. ○ No meaningful difference was seen between treatment groups in AEs (preferred term) of “hypertension” [29/688 (4%) daprodustat vs. 19/404 (4%) rhEPO; 0.91 relative risk (RR) (95% confidence interval: 0.5, 1.67)] or “blood pressure increased” [16 (2%) daprodustat vs. 7 (2%) rhEPO; RR 1.22 (0.48,3.11)]. Results were not substantively different between non-dialysis and haemodialysis subjects. ○ Although no clinically meaningful changes in blood pressure were observed, subjects in both treatment groups required increases in anti-HTN medications: 
 ○ In the 24-week global phase 2b studies, 25/170 (15%) of ND subjects receiving daprodustat vs. 18/80 (14%) control and 22/177 (12%) of HD subjects receiving daprodustat vs. 2/39 (5%) control. ○ In the 52-week Japan phase 3 studies, 57/149 (38%) of ND subjects receiving daprodustat vs. 68/150 (45%) rhEPO and 51/136 (38%) of HD subjects receiving daprodustat vs. 66/135 (49%) for rhEPO. 
The data received to date from completed clinical trials with daprodustat are insufficient to refute this risk.
	
 ● Blood pressure will be closely monitored throughout the dosing period as outlined in the SoA Table Section 2. ● Monitoring of emerging safety data by an internal GSK Safety Review Team.

Potential Risk of Clinical Significance	Summary of Data/Rationale for Risk	Mitigation Strategy

Death, MI, stroke, heart failure, thromboembolic events, thrombosis of vascular access at Hgb levels which are within the normal range (i.e. not polycythemic conditions)
	
Marketed rhEPO/ESAs have been associated with an increased risk for death and serious cardiovascular events when used in patients with anemia of CKD. Clinical studies with marketed rhEPO/analogs have suggested “higher” target hemoglobin, rate of hemoglobin rise of greater than 1 g/dL in any 2-week period, and/or higher doses may contribute to these risks.
 
Integrated AE data from clinical trials with daprodustat [including 2 global phase 2b studies (24-week treatment duration) and 2 Japanese phase 3 studies (52-week treatment duration)]: No meaningful difference was seen between treatment groups in the overall incidence of this AESI: [39/688 (5.5%) daprodustat vs. 25/404 (6%) rhEPO; 0.92 relative risk (95% confidence interval: 0.55, 1.53)]. Within this composite AESI, the most frequent event types were heart failure (at least 12 events daprodustat vs. at least 13 events rhEPO) and thrombosis (at least 14 events daprodustat vs. at least 8 event rhEPO); and a numerical imbalance was noted in events of myocardial ischemia (at least 7 events daprodustat vs. at least 1 event rhEPO). The small number of events makes it difficult to draw any firm conclusions.
 
The data received to date from completed clinical trials with daprodustat are insufficient to substantiate or refute this risk.
	
 • Specific eligibility criteria related to CV risk are outlined in Section 6.2. • Hgb will be closely monitored throughout the dosing period as outlined in the SoA (Section 2). • Monitoring of emerging safety data by an internal GSK Safety Review Team.

Esophageal and gastric erosions
	
In animal studies, undesirable GI effects including emesis, abnormal feces and/or decreased food consumption/body weight loss and stomach erosions/ulcers with hemorrhage were observed with daprodustat.
 
In rodents stomach erosions observed with intravenous and oral administration of daprodustat.
 
Gender-averaged systemic exposure (AUC) at the no observed adverse effect levels (NOAEL) are 3.3 -fold (monkeys) and 737 -fold (rats) above human exposure (25 mg daprodustat).
	
 • Suspected GI bleeding or significant symptoms consistent with erosion should be investigated diagnostically (i.e. endoscopic examination) as clinically warranted. • Monitoring of emerging safety data by an internal GSK Safety Review Team.

Potential Risk of Clinical Significance	Summary of Data/Rationale for Risk	Mitigation Strategy
	
In clinical trials to date with daprodustat, mild-moderate GI signs and symptoms represent the most frequently reported adverse event, however causal association has not been established.
 
Integrated AE data from clinical trials with daprodustat [including 2 global phase 2b studies (24-week treatment duration) and 2 Japanese phase 3 studies (52-week treatment duration)]: No meaningful difference was seen between treatment groups in reports of this AESI [17 (2.7%) daprodustat vs. 10 (2.3%) rhEPO; 1.16 relative risk (95% confidence interval: 0.52, 2.58)].
 
Following review of clinical data received to date, GI erosions have not been identified as a safety concern for daprodustat.
	

Cancer-related mortality and tumor progression and recurrence
	
Marketed rhEPOs have been associated with increased risk of cancer related morbidity and mortality when used in patients with cancer.
 
Administration of 60 mg/kg daprodustat to mice caused minimal increases in circulating VEGF while significant EPO increases were observed.
 
In clinical studies with daprodustat up to 4 weeks duration, a dose-ordered increase in VEGF plasma concentrations, an angiogenic factor that has been implicated in tumor growth, was observed at doses ranging from 10 to 150 mg. In clinical studies up to 24 weeks duration at doses up to 25 mg, changes in VEGF plasma concentrations were variable but similar relative to control.
 
Integrated AE data [including 2 global phase 2b studies (24-week treatment duration) and 2 Japanese phase 3 studies (52-week treatment duration)]: No meaningful difference was seen between treatment groups in the occurrence of this AESI: [8/688 (1.1%) daprodustat vs. 4/404 (0.9%) rhEPO; 1.14 relative risk (95% confidence interval: 0.31, 4.28)].
 
Clinical experience to date is not yet sufficient to substantiate or refute this as a safety concern for daprodustat.
	
 • Specific eligibility criteria related to personal history of malignancy are outlined in Section 6.2. • Stopping criteria for participants with treatment emergent malignancy are outlined in Section 8.2.1. • Monitoring of emerging safety data by an internal GSK Safety Review Team.

Potential Risk of Clinical Significance	Summary of Data/Rationale for Risk	Mitigation Strategy

Pulmonary artery hypertension (PAH)
	
A role for HIF-regulated pathways in the pathophysiology of PAH has been suggested based on well-established effects of acute and chronic hypoxia in man on the pulmonary vasculature (vasoconstriction), and by findings in patients with naturally occurring mutations that result in decreased HIF degradation [Smith, 2006; Formenti, 2011].
 
There have been no histopathologic findings suggestive of PAH in pre-clinical safety studies with daprodustat (up to 13 weeks duration in mice and dog, up to 26 weeks in rat, and up to 39 weeks in monkeys).
 
Acute hypoxic challenge (rats): Daprodustat produced increases in peak right ventricular pressure (PRVP) during acute hypoxia that were slightly higher than the vehicle control group. These hypoxia-induced PRVP changes fall within the range of PRVP differences noted among non-treated rats.
 
Results from a clinical study of acute hypoxic challenge in healthy volunteers demonstrated that short-term (5 days) therapy with daprodustat 5 mg or 100 mg has no clinically significant effect on echocardiographically-estimated systolic pulmonary artery pressure (sPAP) under either normoxic or hypoxic conditions.
 
ECHO assessments performed in Phase 2b studies (24 weeks treatment duration) did not identify any clinically-meaningful changes in sPAP in participants not on dialysis for daprodustat. In hemodialysis participants, mean absolute change from baseline in sPAP was similar for both treatment groups; however, there was a numeric imbalance (Daprodustat: 8 [7%]; Control 0) in participants reaching the sPAP PCI (>20 mmHg increase from baseline). Regarding this imbalance, there were a number of confounding factors in the study, most notably a 4.5:1 randomization scheme and inconsistency in timing of ECHOs relative to dialysis day. Additionally, 2 of 3 participants with resolution of sPAP on safety follow-up ECHOs had confounding conditions that could contribute to resolution other than discontinuation of study treatment; and there was no dose relationship for participants meeting the sPAP PCI
	
 Monitoring of emerging safety data by an internal GSK Safety Review Team.

Potential Risk of Clinical Significance	Summary of Data/Rationale for Risk	Mitigation Strategy
	
criterion. Overall, there is insufficient evidence to conclude a relationship to treatment with daprodustat. A post-hoc analysis was performed using a definition of PAH commonly cited in the literature [Navaneethan, 2016]. Subjects with sPAP >35 mmHg and/or tricuspid regurgitation maximum jet velocity (TRV) >2.5 m/s were considered as having PAH. Regardless of baseline status of PAH, there was no clinically meaningful difference in the proportion of subjects with on-treatment PAH between the two treatment groups:
 
 ○ Subjects with PAH at baseline: 35/113 (31%) vs. 21/54 (39%) (ND) and 37/115 (32%) vs. 7/21 (33%) (HD), daprodustat vs. control, respectively. ○ Subjects without PAH at baseline: 25/113 (22%) vs. 12/54 (22%) (ND) and 22/115 (19%) vs. 6/21 (29%) (HD), daprodustat vs. control, respectively. 
Integrated AE data [including 2 global phase 2b studies (24-week treatment duration) and 2 Japanese phase 3 studies (52-week treatment duration)]: Four (0.5%) non-serious AEs in the daprodustat group vs 0 in rhEPO.
 
 ● Review of subject level information did not suggest adverse treatment effect: 2 subjects from phase2b that met protocol specified stopping criteria on scheduled ECHO had non-serious AEs of ‘pulmonary arterial pressure increased’ and 2 subjects from Japan Phase 3 had non-serious AE ‘pulmonary hypertension’ in setting of concurrent serious AEs of acute pulmonary embolus and mitral regurgitation identified during hospitalization for coronary angiography. 
Following review of clinical data received to date, this has not been identified as a safety concern for daprodustat.
	
Cardiomyopathy	Published data suggest that cardiac effects of HIF stabilization are likely a function of the mechanism, extent, and duration of the effects, and can range from protective to detrimental depending upon the specific model and experimental conditions utilized.	
 ● Monitoring of emerging safety data by an internal GSK Safety Review Team

Potential Risk of Clinical Significance	Summary of Data/Rationale for Risk	Mitigation Strategy
	
Small increases in cardiac troponin in 6 month rat study with daprodustat were consistent with the background finding of spontaneous rodent cardiomyopathy. There were no elevations observed in cardiac troponin in 9 month monkey study with daprodustat.
 
Cardiomyopathy has not been associated with naturally occurring mutation in man which results in increased HIF stabilization.
 
ECHO assessments performed in phase 2b studies (24 weeks treatment duration) did not identify any clinically meaningful changes in LVEF for daprodustat.
 
Integrated AE data from clinical trials with daprodustat [including 2 global phase 2b studies (24-week treatment duration) and 2 Japanese phase 3 studies (52-week treatment duration)]: No meaningful difference was seen between treatment groups in reports of this AESI [1 (0.1%) daprodustat vs. 1 (0.2%) rhEPO; 0.64 relative risk (95% confidence interval: 0.02, 18.07)].
 
Following review of clinical data received to date, this has not been identified as a safety concern for daprodustat.
	

Proliferative retinopathy, macular edema, choroidal neovascularization
	
Increases in local (ocular) VEGF production with retinal neovascularization and macular edema observed in diabetic retinopathy and to choroidal leakage, edema and neovascularization seen in age-related macular degeneration [Campochiaro, 2006].
 
Administration of 60 mg/kg daprodustat to mice caused minimal increases in circulating VEGF while significant EPO increases were observed.
 
No ocular abnormalities with daprodustat were seen in non-clinical studies of up to 13 weeks duration in mice and dogs, 26 weeks in rats, and 39 weeks in monkeys.
 
In clinical studies up to 4 weeks duration, a dose-ordered increase in VEGF plasma concentrations was observed at doses ranging from 10
	
 • Suspected proliferative retinopathy, macular edema, choroidal neovascularization or symptoms consistent with these events should be investigated by ophthalmologic consultation as clinically warranted. • Monitoring of emerging safety data by an internal GSK Safety Review Team.

Potential Risk of Clinical Significance	Summary of Data/Rationale for Risk	Mitigation Strategy
	
to 150 mg. In studies up to 24 weeks duration at doses up to 25 mg, changes in VEGF plasma concentrations were variable but similar relative to control.
 
Ophthalmologic assessments performed in phase 2b studies (24 weeks treatment duration) did not identify any clinically meaningful changes in proliferative retinopathy, macular edema, or choroidal neovascularization with daprodustat.
 
Integrated AE data [including 2 global phase 2b studies (24-week treatment duration) and 2 Japanese phase 3 studies (52-week treatment duration)]: No meaningful difference was seen between treatment groups in reports of this AESI [9 (2.9%) daprodustat vs. 6 (2.5%) rhEPO; 1.19 relative risk; (95% confidence interval: 0.42, 3.43)].
 
Following review of clinical data with daprodustat received to date, this has not been identified as a safety concern for daprodustat.
	

Exacerbation of rheumatoid arthritis
	
In inflamed rheumatic joints, activation of HIF-related genes secondary to decreased oxygen and pro-inflammatory cytokines has been postulated to contribute to the neo-angiogenesis, proliferation and infiltration of rheumatoid synovial fibroblasts [Campochiaro, 2006; Westra, 2010; Muz, 2009].
 
No abnormalities seen in non-clinical studies conducted to date for daprodustat.
 
Integrated AE data [including 2 global phase 2b studies (24-week treatment duration) and 2 Japanese phase 3 studies (52-week treatment duration)]: No meaningful difference was seen between treatment groups in reports of this AESI [2 (0.3%) daprodustat vs. 1 (0.2%) rhEPO; 1.20 relative risk; (95% confidence interval: 0.07, 20.87) and the incidence of musculoskeletal AEs was generally lower in the daprodustat treatment group].
 
Following review of clinical data received to date, this has not been identified as a safety concern for daprodustat.
	
 Monitoring of emerging safety data by an internal GSK Safety Review Team.

Potential Risk of Clinical Significance	Summary of Data/Rationale for Risk	Mitigation Strategy
Drug-drug interactions	
Daprodustat is a substrate of CYP2C8. Co-administration of daprodustat with the strong CYP2C8 inhibitor, gemfibrozil increased the C_{max} and AUC of daprodustat, 4- and 19-fold, respectively, while co-administration of the weak inhibitor, trimethoprim increased the C_{max} and AUC of daprodustat by 1.3- and 1.5-fold, respectively. Population PK analysis from completed Phase 2 studies suggests that co-administration of daprodustat with a moderate CYP2C8 inhibitor (clopidogrel) leads to a ~2-fold increase in AUC, with no clinically-significant increase in the measured Hgb response. Although CYP2C8 induction studies were not performed, coadministration of daprodustat with an inducer of CYP2C8 (e.g., rifampin/rifampicin) may decrease the exposure of daprodustat.
	
 • Co-administration of daprodustat with strong CYP2C8 inhibitors, (e.g., gemfibrozil) and inducers, (e.g., rifampin/rifampicin) is not permitted as outlined in Section 7.7.2. • Specific guidance on the management of potential drug-drug interactions and concomitant medications is provided in Section 7.7. • Hgb will be closely monitored throughout the dosing period as outlined in the SoA in Section 2. • Specific guidance for discontinuation of daprodustat based on achieved Hgb is provided in Section 8.2.1.1. • Monitoring of emerging safety data by an internal GSK Safety Review Team.
Cyst progression in patients with autosomal dominant polycystic kidney disease (ADPKD)	
Published data provide in vivo evidence for a potential role of HIF-1a in the growth of polycystic kidneys; Hif-1a deletion was sufficient to significantly mitigate a progressive polycystic phenotype in an ADPKD mouse model, while conversely pharmacologic HIF-1a stabilization was sufficient to convert a mild polycystic disease into a severely aggravated phenotype with marked loss of renal function. However, the dose of FG-2216 (a PHI) used resulted in a significant erythropoietic response as reflected by ≥10% relative increases in hematocrit over the course of the study. (Kraus, 2018; Hofherr, 2018).
 
A review of the non-clinical data from toxicity studies conducted with daprodustat does not indicate an exacerbation in incidence or severity of kidney cysts in daprodustat-treated animals in comparison to controls. However, the wild type animals used in these toxicity
	
 • Kidney function will be monitored throughout the dosing period as outlined in the SoA (Section 2). • Monitoring of emerging safety data by an internal GSK Safety Review Team.

Potential Risk of Clinical Significance	Summary of Data/Rationale for Risk	Mitigation Strategy
	
studies have a very low background incidence of renal cysts and are not comparable to the mice used in the Kraus article (Kraus, 2018) which are an inducible kidney epithelium-specific Pkd1-deletion model.
 
There is limited experience with daprodustat in subjects with ADPKD in completed clinical trials. In the Japan phase 3 study in non-dialysis subjects, there were 5 subjects with ADPKD (all CKD stage 5) in each treatment group. Mean baseline eGFR was 10 mL/min/1.73m² in the daprodustat subjects vs. 16 mL/min/1.73m² in the rhEPO subjects. The mean (SD) percent change from baseline at Week 52 in eGFR was: -18% (8) vs. -21% (14) in daprodustat vs. rhEPO, respectively.
 
Following review of clinical data received to date, this has not been identified as a safety concern for daprodustat.
	

References

Camposchiaro PA and the first ARVO/Pfizer Institute Working Group *et al.* Ocular versus extraocular neovascularization: Mirror images or vague resemblances. *Invest Ophthalmol & Vis Sci.* 2006; 47:462-474.

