- ¹⁵ SAEs assessed as related to study participation or a GSK product are collected at this visit. See Section 9.2.1 for additional details.

- The timing and number of planned study assessments, including safety or biomarker assessments may be altered during the course of the study based on newly available data to ensure appropriate monitoring.
- Any changes in the timing or addition of time points for any planned study assessments must be documented and approved by the relevant study team member and then archived in the sponsor and site study files but will not constitute a protocol amendment. The IRB/IEC will be informed of any safety issues that require alteration of the safety monitoring scheme or amendment of the ICF.

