6.2. Exclusion Criteria

Participants are excluded from the study if any of the following criteria apply:

Medical Conditions

1. On dialysis or clinical evidence of impending need to initiate dialysis within 90 days after study start (i.e., Day 1).
2. Planned kidney transplant within 3 months after study start.
3. A positive test for HIV antibody.

Prior/Concomitant Therapy

4. History of severe allergic or anaphylactic reactions or hypersensitivity to excipients in the investigational products (see Daprodustat IB for list of excipients).
5. Use of any prescription or non-prescription drugs or dietary supplements that are prohibited from screening until the end of Treatment Period 2 (see Section 7.7.2).
6. Planned or current administration of Mircera (methoxy PEG-epoetin beta).

Prior/Concurrent Clinical Study Experience

7. The participant has participated in a clinical trial and has received an experimental investigational product within the prior 30 days or 5 half lives, whichever is longer, from screening through Day 1.

Diagnostic assessments

8. At or below the lower limit of the reference range at screening for Vitamin B₁₂ (may rescreen in a minimum of 8 weeks).
9. Ferritin outside the range between 100 and 500 ng/mL, inclusive, at screening.
10. Transferrin saturation (TSAT) outside the range between 15% and 40%, inclusive, at Screening.
11. Folate < 2.0 ng/mL (4.5 nmol/L; may rescreen in a minimum of 8 weeks) at screening.
12. High sensitivity C-reactive protein (hsCRP) ≥ 20 µg/mL at screening.

Other Exclusions

13. Myocardial infarction or acute coronary syndrome: ≤ 8 weeks prior to screening through Day 1.
14. Hospitalization for greater than 24 hours: ≤ 8 weeks prior to screening through Day 1
15. Stroke or transient ischemic attack ≤ 8 weeks prior to screening through Day 1.
16. Class IV heart failure, as defined by the New York Heart Association (NYHA) functional classification system.
17. Current uncontrolled hypertension as determined by the investigator.
18. QT interval corrected for heart rate using Bazett's formula (**QTcB**): QTcB > 500 msec, or QTcB > 530 msec in participants with Bundle Branch Block. There is no QTc exclusion for participants with a predominantly paced rhythm.
19. Active chronic inflammatory disease that could impact erythropoiesis. A partial list can be found in the Study Reference Manual (SRM).
20. History of bone marrow aplasia or pure red cell aplasia.

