8.2. Withdrawal from the Study

- A participant may withdraw from the study at any time at his/her own request or may be withdrawn at any time at the discretion of the investigator for safety, behavioral, compliance or administrative reasons.
- If the participant withdraws consent for disclosure of future information, the sponsor may retain and continue to use any data collected before such a withdrawal of consent.
- If a participant withdraws from the study, he/she may request destruction of any samples taken and not tested, and the investigator must document this in the site study records.
- Participants that withdraw/are withdrawn from the study treatment are encouraged to attend the follow-up visit 14 ± 3 days following discontinuation of study treatment. Assessments to be conducted are listed in the SoA (Section 2).

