8.2.1. Criteria for Permanent Discontinuation from Study Treatment and Early Withdrawal

Participants must **permanently discontinue study treatment** and be withdrawn from the study for the following reasons:

- Meets Hgb stopping criteria (See Section 8.2.1.1)
- Meets iron stopping criteria (See Section 8.2.1.2)
- If it becomes medically necessary to adjust the dose of either rhEPO or daprodustat
- Receives a blood transfusion
- Receives a kidney transplant
- Becomes pregnant or intends to become pregnant during the study
- Active GI bleeding
- Diagnosis of cancer, with the exception of squamous cell or basal cell carcinoma
- Liver chemistry abnormalities exceeding the threshold criteria (See Section 8.1.1)
- Use of prohibited medication (See Section 7.7.2)
- Active chronic inflammatory disease that could impact erythropoiesis
- Any new diagnosis of hematological disease including those affecting platelets, white or red blood cells, coagulation disorders, or any other cause of anemia of chronic disease other than renal disease

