8.2.1.1. Hgb Stopping Criteria

GSK will supply a point-of-care Hgb analyzer (HemoCue) to each site for rapid and convenient monitoring of Hgb levels and to ensure consistency of Hgb measurements across sites participating in the study.

Blood samples for measurement of Hgb concentrations via HemoCue will be collected and recorded in the eCRF. [Table 3](#) summarizes the Hgb values and corresponding action to be taken at each visit.

Table 3 Hgb Stopping Criteria

Hgb (g/dL) at visit		Action
<7.5		Repeat HemoCue assessment on the same sample at same study visit to confirm; take average of 2 values. If confirmed, permanently discontinue study treatment and withdraw participant from the study.
≥7.5 - <13.0 With:	≥2.0 g/dL decrease in Hgb over the previous 2 weeks	Repeat HemoCue assessment on the same sample at same study visit to confirm; take average of 2 values. If confirmed, permanently discontinue study treatment and withdraw participant from the study.
≥7.5 - <13.0 With:	<1.0 absolute change in Hgb over the previous 2 weeks	Continue study treatment.
≥7.5 - <13.0 With:	≥1.0 increase in Hgb over the previous 2 weeks	Repeat HemoCue assessment on the same sample at same study visit to confirm; take average of 2 values. If confirmed, permanently discontinue study treatment and withdraw participant from the study.
≥13.0		Repeat HemoCue assessment on the same sample at same study visit to confirm; take average of 2 values. If confirmed, permanently discontinue study treatment and withdraw participant from the study.

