9.2.4. Adverse Events of Special Interest (AESI)

Adverse Events of Special Interest (AESI) have been identified based on non-clinical studies with daprodustat, clinical experience with rhEPOs, and current information regarding HIF-regulated pathways in mediating hypoxia-associated pathophysiology. The currently identified AESI for daprodustat are as follows:

- Thrombosis and/or tissue ischemia secondary to excessive erythropoiesis
- Death, MI, stroke, heart failure, venous thromboembolism, thrombosis of vascular access
- Cardiomyopathy
- Pulmonary artery hypertension
- Cancer-related mortality and tumor progression and recurrence
- Esophageal and gastric erosions
- Proliferative retinopathy, macular edema, choroidal neovascularization
- Exacerbation of rheumatoid arthritis
- Worsening of hypertension

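### Taking vital signs at the existing Day 15 and Day 43 visits would halve the 28-day wait for a blood pressure after each drug switch

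*Protocol*

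**What the plan says.** The worsening-hypertension row of Protocol Appendix 3 gives this mitigation: "Blood pressure will be closely monitored throughout the dosing period as outlined in the SoA Table Section 2". It reports no clinically meaningful blood pressure changes so far, but adds that the completed-trial data "are insufficient to refute this risk". "Worsening of hypertension" is an adverse event of special interest (Protocol 9.2.4), and vital signs assessments are a named safety endpoint (Protocol 4).

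The SoA (Protocol 2) marks vital signs at Week -4, Day 1, Day 29, Day 57 and Day 70. The cells for Week -2, Day 15 and Day 43 are blank. An SoA footnote requires every Day 29 assessment to be done before the crossover. Day 70 is the follow-up visit, after treatment has ended.

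Other relevant provisions:

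- Protocol 6.2 excludes "Current uncontrolled hypertension as determined by the investigator".
- Protocol 8.2.1 lists conditions under which participants must stop treatment "and be withdrawn from the study for the following reasons". Hypertension is not among them.
- Protocol 8.2.1.1 requires withdrawal for a confirmed 1.0 g/dL or greater "increase in Hgb over the previous 2 weeks".
- Under Protocol 8.2, participants who stop early "are encouraged to attend the follow-up visit 14 ± 3 days following discontinuation of study treatment".
- SAP 4.4.3.3 summarises vital signs by sequence and visit and lists values of potential clinical importance (PCI). SAP 6.2.1 sets those limits, for example a systolic rise of more than 30 mmHg from baseline.

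**The concern.** Appendix 3 defines close monitoring only by pointing to the SoA. The SoA gives one scheduled on-treatment blood pressure per 28-day period, taken at its end. After a change of drug, nothing is scheduled during the first four weeks.

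This applies to daprodustat in all four sequences and to the return to rhEPO in Sequences C and D. It does not apply to Period 1 rhEPO in Sequences A and B, where the Week -4 and Day 1 readings are already on the participant's stable rhEPO.

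Two things are at stake. First, a participant withdrawn at Day 15 or Day 43, for instance under the Hgb-rise rule, leaves with no scheduled blood pressure on the new drug. The next scheduled one is at a visit they are only encouraged to attend, when they are off that drug. Second, the PCI limits in the SAP can be applied to scheduled on-treatment readings only at Days 29 and 57.

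**Working it through.** **Reading the schedule.** The SoA has eight columns: Week -4, Week -2, and Days 1, 15, 29, 43, 57 and 70. Column placement can be checked against rows whose timing is known. Isotope administration and liver chemistry fall only on Days 15 and 43. Weight is marked at Week -4 and Days 1, 15 and 43, which agrees with the Day 15 and Day 43 weights used in SAP 4.2.1. Both visits therefore already exist, with blood draws.

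Appendix 3 describes Hgb monitoring for excessive erythropoiesis in nearly the same terms as blood pressure, again by reference to the SoA. On-treatment visits in the SoA:

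| Measure | Day 15 | Day 29 | Day 43 | Day 57 |
|---|---|---|---|---|
| HemoCue Hgb | yes | yes | yes | yes |
| Vital signs | no | yes | no | yes |

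**Gap from switch to first scheduled on-drug blood pressure.** The nominal gap now is 29 − 1 = 28 days and 57 − 29 = 28 days, which matches the stated 28-day periods. With the added readings it is 15 − 1 = 14 and 43 − 29 = 14 days. The treatment-period window is ±2 days. Day 1 is taken as the anchor for the first switch; for the Day 29 switch the window applies at both ends.

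| Switch | Now | With Days 15 and 43 |
|---|---|---|
| Day 1 | 28 ± 2 = 26 to 30 days | 14 ± 2 = 12 to 16 days |
| Day 29 | 28 ± 4 = 24 to 32 days | 14 ± 4 = 10 to 18 days |

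**Number of readings.** Take 12 completers, three per sequence.

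- Switches: 6 × 1 in A and B (Day 29) + 6 × 2 in C and D (Days 1 and 29) = 18.
- Post-switch blood pressure time points: 18 × 1 = 18 now, 18 × 2 = 36 with the change.
- Time points added in all: 12 × 2 = 24. Of these, 18 follow a switch and 6 are Day 15 readings on continuing rhEPO in A and B.

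**Early withdrawals.** The follow-up visit falls 14 ± 3 = 11 to 17 days after stopping. The documents give no withdrawal rate at 1 to 4 mg. As an assumption, let 5%, 10% or 20% of switches end in withdrawal at the two-week visit. Per 18 switches started, 18 × 0.05 = 0.9, 18 × 0.10 = 1.8 or 18 × 0.20 = 3.6 would have no scheduled on-drug blood pressure.

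**How often blood pressure would need action.** Appendix 3 gives counts of non-dialysis daprodustat participants who needed more antihypertensive medication: 25/170 over 24 weeks and 57/149 over 52 weeks. Assuming a constant rate, the four-week probability is 1 − exp[(4/T) × ln(1 − p)]:

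- 24-week studies: 1 − exp[(4/24) × ln(1 − 25/170)] = 0.026, or 0.31 of 12 participants.
- 52-week study: 1 − exp[(4/52) × ln(1 − 57/149)] = 0.036, or 0.44 of 12 participants.
- 52-week study, rhEPO comparator (68/150): 1 − exp[(4/52) × ln(1 − 68/150)] = 0.045.

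The comparator rate is no lower than the daprodustat rates. The 0.3 to 0.4 participants are therefore background escalation of treatment, not an excess caused by switching.

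**The case against.** The strongest reply is that no error is alleged. The SoA is followed, any schedule can be made denser, and Amendment 1 already revised the vital-signs time points for fuller monitoring, so the spacing may be deliberate. That is fair, and it is why this is offered only as an improvement.

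A second reply is that other safeguards exist:

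- Investigators must monitor clinical status to standard-of-care level (Protocol 7.7.3).
- They may withdraw a participant for safety at any time (8.2).
- They must raise immediate safety concerns with the sponsor (9).
- An internal Safety Review Team follows emerging data (Appendix 3).
- Unscheduled readings enter worst-case derivations and listings (SAP 6.2.4).

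These limit the consequence, but none of them schedules a reading.

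Third, nothing in the documents shows added hazard in the first 14 days. Appendix 3 reports hypertension events in 29/688 on daprodustat against 19/404 on rhEPO (relative risk 0.91), and the rhEPO escalation rate above is the higher one. This stands as a limit on the expected benefit. The protocol nevertheless treats the risk as open.

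Fourth, six of the 18 switches are returns to the participant's own earlier rhEPO dose, so only 12 are to the investigational drug. The withdrawal percentages have no source in the documents. A Sequence C or D participant withdrawn at Day 15 also never makes the Day 29 switch, which is why the counts are per 18 switches started. These points are correct and lower the weight of the totals. They do not change the 28-day gap.

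**Conclusion.** The point holds as a low-cost improvement. After each switch there is one scheduled on-treatment blood pressure, a nominal 28 days later. Two added SoA marks would make it 14 days and would double post-switch time points from 18 to 36 in 12 completers.

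The schedule, gaps and counts follow directly from the SoA and the sequence table. The 0.3 to 0.4 participants per 28 days rest on a constant rate and describe background escalation. The 0.9 to 3.6 switches without a reading rest on assumed withdrawal rates.

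The consequence is limited. Adverse events and concomitant medications are reviewed at Days 15 and 43, so symptomatic hypertension or a change in antihypertensives would be recorded. A sustained rise would still be seen at Day 29 or Day 57 in those who continue. The primary endpoint and its power are not affected.

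**What to change.** Mark vital signs at Day 15 and Day 43 in the SoA, taken before the blood draw as Protocol 9.4.3 already requires.

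The cost is five minutes of rest and three seated readings at visits already planned: 24 extra time points in 12 completers and no new visit. The SAP needs no change, because 4.4.3.3 already summarises vital signs by visit and lists all values and PCI values, and 6.2.4 displays every scheduled visit.

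The change must be documented and approved. The SoA notes say that changes in timing or added time points must be archived "but will not constitute a protocol amendment". The same notes link alterations to newly available data, however, so the sponsor may judge that an amendment is needed. The worst case is an amendment to one SoA row, with IRB/IEC approval before implementation and re-consent if the consent form is updated (Protocol Appendix 5).
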